5.3.2 Eliciting Adverse Event Information

A consistent methodology of non-directive questioning should be adopted for eliciting adverse event information at all patient evaluation timepoints. Examples of non-directive questions include the following:

"How have you felt since your last clinic visit?"

"Have you had any new or changed health problems since you were last here?"

5.3.3 Assessment of Severity of Adverse Events

The adverse event severity grading scale for the NCI CTCAE (v5.0) will be used for assessing adverse event severity. [Table 3](#) will be used for assessing severity for adverse events that are not specifically listed in the NCI CTCAE.

Table 3 Adverse Event Severity Grading Scale for Events Not Specifically Listed in NCI CTCAE

Grade	Severity
1	Mild; asymptomatic or mild symptoms; clinical or diagnostic observations only; or intervention not indicated
2	Moderate; minimal, local, or non-invasive intervention indicated; or limiting age-appropriate instrumental activities of daily living ^a
3	Severe or medically significant, but not immediately life-threatening; hospitalization or prolongation of hospitalization indicated; disabling; or limiting self-care activities of daily living ^{b, c}
4	Life-threatening consequences or urgent intervention indicated ^d
5	Death related to adverse event ^d

NCI CTCAE = National Cancer Institute Common Terminology Criteria for Adverse Events.

Note: Based on the most recent version of NCI CTCAE (v5.0), which can be found at:
http://ctep.cancer.gov/protocolDevelopment/electronic_applications/ctc.htm

^a Instrumental activities of daily living refer to preparing meals, shopping for groceries or clothes, using the telephone, managing money, etc.

^b Examples of self-care activities of daily living include bathing, dressing and undressing, feeding oneself, using the toilet, and taking medications, as performed by patients who are not bedridden.

^c If an event is assessed as a "significant medical event," it must be reported as a serious adverse event (see Section 5.4.2 for reporting instructions), per the definition of serious adverse event in Section 5.2.2.

^d Grade 4 and 5 events must be reported as serious adverse events (see Section 5.4.2 for reporting instructions), per the definition of serious adverse event in Section 5.2.2.

5.3.4 Assessment of Causality of Adverse Events

Investigators should use their knowledge of the patient, the circumstances surrounding the event, and an evaluation of any potential alternative causes to determine whether an adverse event is considered to be related to the study drug, indicating "yes" or "no" accordingly. The following guidance should be taken into consideration (see also [Table 4](#)):

- Temporal relationship of event onset to the initiation of study drug
- Course of the event, with special consideration of the effects of dose reduction, discontinuation of study drug, or reintroduction of study drug (as applicable)
- Known association of the event with the study drug or with similar treatments
- Known association of the event with the disease under study
- Presence of risk factors in the patient or use of concomitant medications known to increase the occurrence of the event
- Presence of non-treatment-related factors that are known to be associated with the occurrence of the event

Table 4 Causal Attribution Guidance

Is the adverse event suspected to be caused by the study drug on the basis of facts, evidence, science-based rationales, and clinical judgment?	
YES	There is a plausible temporal relationship between the onset of the adverse event and administration of the study drug, and the adverse event cannot be readily explained by the patient's clinical state, intercurrent illness, or concomitant therapies; and/or the adverse event follows a known pattern of response to the study drug; and/or the adverse event abates or resolves upon discontinuation of the study drug or dose reduction and, if applicable, reappears upon re-challenge.
NO	An adverse event will be considered related, unless it fulfills the criteria specified below. Evidence exists that the adverse event has an etiology other than the study drug (e.g., preexisting medical condition, underlying disease, intercurrent illness, or concomitant medication); and/or the adverse event has no plausible temporal relationship to administration of the study drug (e.g., cancer diagnosed 2 days after first dose of study drug).

5.3.5 Procedures for Recording Adverse Events

Investigators should use correct medical terminology/concepts when recording adverse events on the Adverse Event eCRF. Avoid colloquialisms and abbreviations.

Only one adverse event term should be recorded in the event field on the Adverse Event eCRF.

5.3.5.1 Diagnosis versus Signs and Symptoms

A diagnosis (if known) should be recorded on the Adverse Event eCRF rather than individual signs and symptoms (e.g., record only liver failure or hepatitis rather than

jaundice, asterixis, and elevated transaminases). However, if a constellation of signs and/or symptoms cannot be medically characterized as a single diagnosis or syndrome at the time of reporting, each individual event should be recorded on the Adverse Event eCRF. If a diagnosis is subsequently established, all previously reported adverse events based on signs and symptoms should be nullified and replaced by one adverse event report based on the single diagnosis, with a starting date that corresponds to the starting date of the first symptom of the eventual diagnosis.

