3.3.5 Rationale for Non-Standard Clinical Outcome Assessments

At the onset of the COVID-19 pandemic, there was limited understanding of what constituted disease progression in COVID-19 and how the symptoms were manifested and impacted patients' lives. Given the heterogeneous nature of COVID-19–related symptoms in outpatients, key COVID-19–related symptoms should be assessed systematically to provide an accurate evaluation. Currently, there are no validated patient-reported outcome (PRO) tools for the assessment of COVID-19 symptoms. This study will utilize a PRO instrument based on the example U.S. Food and Drug Administration (FDA) COVID-19 PRO instrument that assesses 14 of the most common COVID-19 symptoms (FDA 2020). The symptom items used in this PRO are derived from information provided by the Centers for Disease Control and Prevention (CDC) as of 28 August 2020.

4. **MATERIALS AND METHODS**

4.1 **PATIENTS**

Up to approximately 404 non-hospitalized adult patients with mild or moderate COVID-19 will be enrolled in this study.

4.1.1 **Inclusion Criteria**

Patients must meet the following criteria for study entry:

- Signed Informed Consent Form
- Age ≥ 18 years at time of signing Informed Consent Form
- Willing and able to comply with the study protocol and all study procedures, in the opinion of the investigator
- Positive SARS-CoV-2 diagnostic test (RT-PCR or rapid antigen test) at screening
- Has symptoms consistent with mild or moderate COVID-19, as determined by the investigator, with onset ≤ 5 days prior to randomization
- For women of childbearing potential: agreement to remain abstinent (refrain from heterosexual intercourse) or use adequate contraception during the treatment period and for 30 days after the final dose of study drug.

A woman is considered to be of childbearing potential if she is postmenarchal, has not reached a postmenopausal state (≥ 12 continuous months of amenorrhea with no identified cause other than menopause), and is not permanently infertile due to surgery (i.e., removal of ovaries, fallopian tubes, and/or uterus) or another cause as determined by the investigator (e.g., Müllerian agenesis). The definition of childbearing potential may be adapted for alignment with local guidelines or regulations. Women of childbearing potential must be established on their chosen method of contraception at screening.

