5.3.5.3 Persistent or Recurrent Adverse Events

A persistent adverse event is one that extends continuously, without resolution, between patient evaluation timepoints. Such events should only be recorded once on the Adverse Event eCRF. The initial severity (intensity or grade) of the event will be recorded at the time the event is first reported. If a persistent adverse event becomes more severe, the most extreme severity should also be recorded on the Adverse Event eCRF. If the event becomes serious, it should be reported to the Sponsor immediately (i.e., no more than 24 hours after learning that the event became serious; see Section 5.4.2 for reporting instructions). The Adverse Event eCRF should be updated by changing the event from "non-serious" to "serious," providing the date that the event became serious, and completing all data fields related to serious adverse events.

A recurrent adverse event is one that resolves between patient evaluation timepoints and subsequently recurs. Each recurrence of an adverse event should be recorded as a separate event on the Adverse Event eCRF.

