5.4.2 Reporting Requirements for Serious Adverse Events and Adverse Events of Special Interest

5.4.2.1 Events That Occur prior to Study Drug Initiation

After informed consent has been obtained but prior to initiation of study drug, only serious adverse events caused by a protocol-mandated intervention should be reported. The paper Clinical Trial Serious Adverse Event/Adverse Event of Special Interest Reporting Form provided to investigators should be completed and submitted to the Sponsor or its designee immediately (i.e., no more than 24 hours after learning of the event), either by faxing or by scanning and emailing the form using the fax number or email address provided to investigators.

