5.4.2.2 Secondary Endpoints (Safety)

The safety objective for this study is to evaluate the safety of AT-527 compared with placebo.

The safety population will be used for all safety analyses. Patients will be analyzed according to the treatment they actually received.

Safety analyses will be presented by each AT-527 dose and a combined placebo group containing patients from all cohorts. Safety will be assessed through summaries of exposure to study treatment, AEs, changes in laboratory test results, and changes in vital signs and ECGs. If a low number of events is observed, a listing may be produced in place of a summary table. A listing of pregnancies will also be produced.

Study treatment exposure (such as treatment duration and total dose received) will be summarized with descriptive statistics.

- **Incidence and severity of AEs, with severity determined according to NCI CTCAE v5.0**

All verbatim AE terms will be mapped to Medical Dictionary for Regulatory Activities (MedDRA) thesaurus terms and will be classified by System Organ Class (SOC) and preferred term. AE severity will be graded according to NCI CTCAE v5.0. For AEs of varying severity, the highest grade will be used in the summaries. Deaths and cause of death will be listed.

Only treatment-emergent AEs will be summarized. Treatment-emergent AEs are defined as those AEs with observed or imputed onset date on or after the start date of trial treatment. Only where the most extreme intensity is greater than the initial intensity (or if most extreme intensity is not missing and initial intensity is missing) will events with an onset date prior to the start of study treatment be considered treatment-emergent.

An AE with a completely missing start date will be assumed to be treatment-emergent unless the AE has a complete non-imputed end date that is prior to study Day 1. AEs will be coded and tabulated by SOC and/or Preferred Terms (PTs). In tabulations, PTs

and their associated SOC will be presented in order of descending frequency summed across the treatment groups.

The following will be summarized for each AT-527 group and a pooled placebo group, and listings produced where required:

- AEs
- SAEs
- AEs related to study treatment
- AEs leading to death
- AEs leading to withdrawal of study drug
- AEs leading to withdrawal from study
- AEs occurring in $\geq 5\%$ of patients in at least one treatment group
- AEs occurring in $\geq 10\%$ of patients in at least one treatment group

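### A diagnosis dated back to a pre-dose COVID-19 symptom and entered at one unchanging grade drops out of the treatment-emergent adverse event summaries

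*Protocol*

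**What the plan says.** **Recording.** When a diagnosis is established after its signs or symptoms have been reported, Protocol 5.3.5.1 cancels those entries and puts one diagnosis entry in their place. The new entry is made "with a starting date that corresponds to the starting date of the first symptom of the eventual diagnosis". Protocol 5.3.5.3, on persistent events, adds: "The initial severity (intensity or grade) of the event will be recorded at the time the event is first reported". If the event later worsens, the highest grade is recorded as well.

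**Population.** Protocol 4.1.1 admits a patient who "Has symptoms consistent with mild or moderate COVID-19, as determined by the investigator". The symptoms must have begun no more than 5 days before the patient is randomized. The diary in Protocol Appendix 5 includes cough, shortness of breath, fatigue and nausea.

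**Before dosing.** Under Protocol 5.4.2.1 (and 5.3.1), "only serious adverse events caused by a protocol-mandated intervention should be reported".

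**Analysis.** SAP 5.4.2.2 states: "Only treatment-emergent AEs will be summarized". An onset on or after the start of treatment qualifies outright. Otherwise, only where the highest grade exceeds the initial grade, or the initial grade is missing and the highest is not, "will events with an onset date prior to the start of study treatment be considered treatment-emergent". An entry with no start date at all is assumed to be treatment-emergent unless a complete end date falls before Day 1. Protocol 6.5 limits its AE summaries to events from the first dose onward and states no exception for worsening.

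**The concern.** The recording rule and the analysis filter were written separately and can work against each other. In many trials the first symptom of a diagnosis made on treatment also falls on treatment. Here every patient is symptomatic at entry, and the symptoms overlap with the early signs of conditions that a safety analysis needs to count, such as pneumonia, respiratory failure and hepatitis. A diagnosis made after dosing can therefore be given a start date before dosing. The SAP filter may then treat it as a condition that the patient brought into the trial.

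Incidence and severity of AEs is a secondary endpoint, and it is the one that supports the comparison of safety with placebo. Severe events of this kind should be few, so losing even one matters.

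**Working it through.** No stated figure needs reproducing. The check follows one event through the rules and then enumerates the SAP filter.

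**1. Is a pre-dose date possible?** Suppose a patient has a cough before dosing. After dosing, breathlessness worsens more than the investigator expected and is entered as an AE. Pneumonia is then diagnosed at Grade 3. The breathlessness entry is nullified and one pneumonia entry takes its place. Protocol 5.3.5.1 permits two readings of its start date:
- the date of the earliest AE entry being replaced, which is after dosing, so the event is treatment-emergent;
- the date of the first symptom of the pneumonia, taken literally, which may be the pre-dose cough.

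The text refers to the first symptom. It does not limit this to symptoms after dosing or to symptoms previously entered as AEs.

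**2. Which initial grade does the replacement entry carry?** Neither document says. Protocol 5.3.5.3 ties the initial grade to the time of first report. For a new diagnosis entry this can be read as the grade at diagnosis. It can also be read as the grade of the milder symptom entry it replaced.

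**3. The SAP filter for a pre-dose onset.** Let *i* be the initial grade and *e* the highest grade. The event is kept if *e* > *i*, or if *i* is missing and *e* is present. Otherwise it is dropped. For each *e* from 1 to 5, *i* may be 1 to *e* or missing, which gives *e* + 1 combinations.

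| Highest grade *e* | Combinations | Kept | Dropped (*i*, *e*) |
|---|---|---|---|
| 1 | 2 | 1 | (1,1) |
| 2 | 3 | 2 | (2,2) |
| 3 | 4 | 3 | (3,3) |
| 4 | 5 | 4 | (4,4) |
| 5 | 6 | 5 | (5,5) |
| All | 20 | 15 | 5 |
| 3 to 5 | 15 | 12 | 3 |

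These are counts of rule combinations, not expected patient frequencies. Loss occurs exactly where the two grades are equal. In the example, an entry with initial Grade 1 and highest Grade 3 is kept, while an entry at Grade 3 throughout is dropped.

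**4. Protocol 6.5 taken alone.** With no worsening exception stated, an event dated before the first dose would not be summarised whatever its grades. The two documents therefore differ on the same event.

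**5. What else does the filter do?** Only procedure-caused serious AEs are reported before dosing. Most AE entries with a pre-dose onset would therefore be post-dose reports that were dated back, which are the entries at issue. Meanwhile an entry with no date is counted by default.

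**6. Size per event.** Planned arms are 30 patients (60/2 in Cohort A; 40 × 3/4 active in each of Cohorts B–D) or 112 (224/2 in Cohort E). If all are dosed, one lost event changes the reported incidence by 1/30 = 3.3 or 1/112 = 0.9 percentage points.

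**The case against.** The strongest reply is that several things must coincide. Back-dating is prescribed only when sign or symptom AEs are being replaced, and pre-dose COVID-19 symptoms are not normally AE entries. Anticipated COVID-19 symptoms are kept off the AE form (Protocol 5.3.5.9), and pre-existing conditions are entered only if they worsen (5.3.5.8). A site could reasonably use the date of the earliest replaced entry. If it carries over a milder initial grade, the worsening exception saves the event. All of this stands, and it limits the problem to a conditional one.

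Other outputs also help. Deaths have their own listing and frequency table. SAP Table 8 counts ALT, AST and bilirubin elevations from laboratory values. The complications endpoint in SAP 5.4.2.3 counts radiologically confirmed pneumonia, acute respiratory failure and hospitalization. The SAP says that all AEs of special interest will be presented. A reader might infer that serious diagnoses vanish from every safety output, or that only deaths are tabulated elsewhere. The documents do not support either inference. These outputs are still not full substitutes. The complications endpoint is an efficacy summary in the mITTi population, Table 8 captures laboratory values rather than diagnoses, and the SAP does not say whether the treatment-emergent restriction applies to events of special interest.

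Protocol 5.3.5.2 has medically significant secondary events recorded independently when separated in time, and 5.3.5.9 has unexpected worsening of COVID-19 recorded. Both decide whether an entry is made. Neither fixes its start date or its initial grade.

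Finally, the only in-trial safety data quoted (Protocol 5.1.1, first 30 patients of Cohort A) showed Grade 1 or 2 AEs only and no serious AEs. That is fair context for how often severe events arise, but it does not settle the rule for larger cohorts or other doses.

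**Conclusion.** The point holds conditionally. It needs a site to date a replacement diagnosis to a pre-dose symptom and to enter equal initial and highest grades. The event is then excluded from the treatment-emergent AE, serious AE and Grade 3 or higher summaries. Both steps are allowed by the text, and neither is required by it.

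Two stronger readings are tempting. One is that the SAP discards every event dated before dosing. It does not, because the same paragraph keeps events that worsened and events with no initial grade. The other is that the rule favours AT-527. Site staff are blinded and the rule is the same in both arms, so no direction of bias is shown. What can be said is that affected events are undercounted.

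The loss per affected event is complete within those summaries. How many events would be affected cannot be derived from the documents. Since the alternative rule is simple and nearly free, the change should be made.

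**What to change.** - **SAP 5.4.2.2:** treat as treatment-emergent any AE first reported after the first dose, except a serious AE that a protocol procedure caused before dosing. The onset-time categories start at Day 1, so say how an entry still carrying a pre-dose date is placed, for example by date of diagnosis or of first post-dose worsening.
- **Protocol 6.5:** align the wording with that definition.
- **Protocol 5.3.5.1:** add that symptoms present before the first dose do not set the start date of a diagnosis made after it.

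The cost is one SAP rule, one matching edit to Protocol 6.5 and one clarifying sentence for sites. The small downside is that a few conditions that truly began before dosing will be counted as treatment-emergent, which is the conservative direction for a safety summary.

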5.3.5.2 Adverse Events that Are Secondary to Other Events

In general, adverse events that are secondary to other events (e.g., cascade events or clinical sequelae) should be identified by their primary cause, with the exception of severe or serious secondary events. A medically significant secondary adverse event that is separated in time from the initiating event should be recorded as an independent event on the Adverse Event eCRF. For example:

- If vomiting results in mild dehydration with no additional treatment in a healthy adult, only vomiting should be reported on the eCRF.
- If vomiting results in severe dehydration, both events should be reported separately on the eCRF.
- If a severe gastrointestinal hemorrhage leads to renal failure, both events should be reported separately on the eCRF.
- If dizziness leads to a fall and consequent fracture, all three events should be reported separately on the eCRF.
- If neutropenia is accompanied by an infection, both events should be reported separately on the eCRF.

All adverse events should be recorded separately on the Adverse Event eCRF if it is unclear as to whether the events are associated.

5.3.5.3 Persistent or Recurrent Adverse Events

A persistent adverse event is one that extends continuously, without resolution, between patient evaluation timepoints. Such events should only be recorded once on the Adverse Event eCRF. The initial severity (intensity or grade) of the event will be recorded at the time the event is first reported. If a persistent adverse event becomes more severe, the most extreme severity should also be recorded on the Adverse Event eCRF. If the event becomes serious, it should be reported to the Sponsor immediately (i.e., no more than 24 hours after learning that the event became serious; see Section 5.4.2 for reporting instructions). The Adverse Event eCRF should be updated by changing the event from "non-serious" to "serious," providing the date that the event became serious, and completing all data fields related to serious adverse events.

A recurrent adverse event is one that resolves between patient evaluation timepoints and subsequently recurs. Each recurrence of an adverse event should be recorded as a separate event on the Adverse Event eCRF.

5.3.5.4 Abnormal Laboratory Values

Not every laboratory abnormality qualifies as an adverse event. A laboratory test result must be reported as an adverse event if it meets any of the following criteria:

- Is accompanied by clinical symptoms
- Results in a change in study treatment (e.g., dosage modification, treatment interruption, or treatment discontinuation)
- Results in a medical intervention (e.g., potassium supplementation for hypokalemia) or a change in concomitant therapy
- Is clinically significant in the investigator's judgment

It is the investigator's responsibility to review all laboratory findings. Medical and scientific judgment should be exercised in deciding whether an isolated laboratory abnormality should be classified as an adverse event.

If a clinically significant laboratory abnormality is a sign of a disease or syndrome (e.g., ALP and bilirubin $5 \times$ ULN associated with cholestasis), only the diagnosis (i.e., cholestasis) should be recorded on the Adverse Event eCRF.

If a clinically significant laboratory abnormality is not a sign of a disease or syndrome, the abnormality itself should be recorded on the Adverse Event eCRF, along with a descriptor indicating whether the test result is above or below the normal range (e.g., "elevated potassium," as opposed to "abnormal potassium"). If the laboratory abnormality can be characterized by a precise clinical term per standard definitions, the clinical term should be recorded as the adverse event. For example, an elevated serum potassium level of 7.0 mEq/L should be recorded as "hyperkalemia."

Observations of the same clinically significant laboratory abnormality from visit to visit should only be recorded once on the Adverse Event eCRF (see Section [5.3.5.3](#) for details on recording persistent adverse events).

